PART 1: SOCIO-DEMOGRAPHIC CHARACTERISTICS

1. Age (in completed years).....

2. Gender:

Male Female Others (specify).....

3. Ethnicity

- a. Brahmin/chhetri
- b. Newar
- c. Mongolian
- d. Dalit
- e. Terai region
- f.

4. Occupation

- a. Agriculture
- b. Service
- c. Labor
- d. House maker
- e. Student

5. Food habit

- a. Vegetarian
- b. Non-Vegetarian

6. Smoking Habit

- a. Yes
- b. No

7. Alcohol Intake

- a. Non-alcoholic
- b. Moderate
- c. Significant

Part 2: Information related to Clinical profile of the patient

1. Mode of presentation

- a. Cholangitis
- b. Obstructive Jaundice
- c. Non-icteric Cholestasis

2. Comorbidity

- a. Yes
- b. No

3. Symptoms

- a. Itching
- b. Abdominal Pain
- c. Asymptomatic Jaundice
- d. Anorexia
- e. Weight loss

4. Investigations

- a. USG
- b. CT Scan
- c. MRI
- d. MRCP
- e. EUS

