- Study using stored specimens/tissue
- Study using stored medical records
- Others.....

A.7 Is study single center or multicenter

- Single center
- Multicenter (within Nepal)
Please specify the study sites
- Multicenter (International)
Please specify the study sites

Note: NHRC Approval is compulsory for Ph. D/ International Study/ International Collaboration/ Multicenter & Clinical Trial Study.

A.8 Summary of the proposed research protocol (within 200 words)

Cholangiocarcinoma (CCA) or a bile duct cancer is regarded as the second most frequent type of primary liver cancer which is diagnosed in the late decades of life with fatal outcomes. Its risk factors include primary sclerosing cholangitis, hepatitis, smoking, alcohol, obesity, inflammatory bowel disease, cirrhosis, etc. As it is a fatal disease with late diagnosis, knowing the risk factors and its occurrence rate will be helpful to design interventions based on the evidence. It is also important for the early treatment and increased survival rate of patients. It is a quantitative observational type of study. The objective of this study is to collect the clinico-demographic profile of the patients with cholangiocarcinoma undergoing Endoscopic Retrograde Cholangiopancreatography (ERCP) in Dhulikhel Hospital. Self- structured Questionnaire will be used as a research tool for data collection based on literature review. This kind of research is crucial to widen the knowledge in prevention of the morbidity and mortality due to cholangiocarcinoma. Dhulikhel Hospital is a pioneer tertiary care center in Nepal for ERCP, where cases are from different parts of Nepal and their medical records will be reviewed to generate the

evidence of the clinico-demographic profile of the patient with cholangiocarcinoma undergoing ERCP.

A.9 Source of Funding/Sponsor

Non Funded

A.11 Declaration of Co-I

None

B. DETAIL OF THE STUDY

B.1. Background:

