Bile is a complex aqueous secretion that originates from hepatocytes of liver then stored and concentrated in gallbladder or is delivered directly to the intestinal lumen whose function is to break down fats and help the body to remove excretory products.¹ Bile duct is a tube which connects gallbladder and liver to the small intestine to allow flow of bile into the small intestine.¹ Cholangiocarcinoma (CCA) is an epithelial cell malignancy of biliary tree that arises from varying locations.² Of three types i.e Extra hepatic, Hilar and Intra hepatic cholangiocarcinoma, Extra hepatic is the most common and most treatable form of cholangiocarcinoma.³⁻⁵ Risk factors include primary sclerosing cholangitis, hepatitis, smoking, alcohol, obesity, inflammatory bowel disease, cirrhosis, host genetic polymorphisms, etc.⁶

Discussing the data of cholangiocarcinoma, these are most common in Southeast and East Asia due to the prevalence of parasitic infection in those particular areas as it is one of the important causes of cholangiocarcinoma.⁷ *Ophisthorchis Viverrini* and *Clonorchis sinensis* are the hepatobiliary flukes mainly associated with CCA in Southeast Asia.⁶ A study done in the United States stated the continued increment in incidence of cholangiocarcinoma from 2001-2017 with greater increase in intrahepatic CCA than extrahepatic CCA.⁸ Different liver flukes are also associated with cholangiocarcinoma in countries like Vietnam, Thailand, Korea, China, Vietnam, etc.⁷

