Nepal being an Asian country is also in the region to have increased cases of cholangiocarcinoma and need rigorous scientific studies to generate evidence to prepare interventions on its prevention and treatment. Cholangiocarcinoma being the major contributing factor for the death of the humans, this needs early diagnosis and treatment system to intrude the increasing mortality and morbidities. Studies should be conducted in its risk factors, disease status, occurrence and other factors so that such studies are considered to estimate the prevention and management of such deadly diseases.

The studies on this sector is in dearth and is in great need of the involvement of academia, medical centers and different institutions. Such studies will provide evidence to plan several interventions for its better and efficient prevention and treatment option.

B.3. Research hypothesis (if applicable):

NA

B.4. Objectives of the research:

General objective (s)

The aim of the study is to assess the clinico-demographic profile of the patient with cholangio-carcinoma undergoing ERCP in Dhulikhel Hospital.

Specific objective(s):

This study holds the objective,

- To identify clinical profile of the patient with cholangio-carcinoma undergoing ERCP
- To describe the demographic profile of the patient with cholangio-carcinoma undergoing ERCP
- To measure the outcome of ERCP procedure in them.
- To identify the association between demographic variable and clinical presentation of the patient with cholangio-carcinoma undergoing ERCP

B.5. Study site and justification:

The study will be conducted in the Endoscopy unit of the Internal medicine department of Dhulikhel Hospital. This hospital has provided services to more than 50 out of 75 districts of the country. It provides services to about 2.7 million people from Kavrepalanchowk, Sindhupalchowk, Dolakha, Lalitpur, Kathmandu, Sindhuli, Ramechhap and other surrounding districts per-year. In Nepal ERCP procedure has been limited to very few Tertiary centers and Dhulikhel Hospital is the pioneer institute to provide the ERCP procedure (since 2011) in the nation. This procedure is mainly performed for the indication of choledocolithiasis, obstructive Jaundice, acute biliary pancreatitis, cholangiocarcinoma, etc. In 2019 only, a total of 1352 patients had undergone ERCP in Dhulikhel Hospital as per the monthly ERCP report book obtained from the Department of Endoscopy of Dhulikhel Hospital.

B6. METHODS/ METHODOLOGY:

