B.6.1 Research Methods (Cross in the appropriate box)

a) Qualitative Research Quantitative Research c) Mixed Research

B.6.2. Study design:

This is a quantitative, retrospective, descriptive cross-sectional observational study.. The outcome and the exposure will be measured at the same time as a snapshot.

B.6.3. Study Variables

The study variables will be the socio-demographic variables and the clinical details of the study participants.

B.6.4. Expected outcomes of the research

The expected outcome of the research is to present a clinical finding of this under studied clinical area in Nepal. Furthermore, this will be a reference for the future researchers to conduct further studies on this sector to enhance the prevention, management and the treatment services.

B.7 STUDY POPULATION AND SAMPLE

B.7.1. Participants/ study population:

Patients with cholangiocarcinoma who had undergone ERCP in Endoscopic Department of Dhulikhel Hospital. The patient's information will be obtained from patients' medical records from the outpatient and inpatient department of Dhulikhel Hospital. Thus, the person will not be contacted directly for the data collection.

B.7.2 Selection criteria:

Inclusion criteria:

- All the participants with cholangiocarcinoma had undergone ERCP
- above 18 years of age.

Exclusion criteria:

- ERCP failed cases

B.7.3. Sampling method/ technique:

We will do purposive sampling from the eligible list obtained from the medical records.

B.7.4. Sampling Unit:

The sampling unit is the patient with cholangiocarcinoma who had undergone ERCP.

B.7.5 Sample size determination:

All the eligible cases listed in the medical record of Dhulikhel Hospital from January 2017 to January 2023. Hospital records showed approximately 75 cases of cholangiocarcinoma per year. So, we will conduct a total population sampling with an estimated sample size of 375.

B.8. Procedure:

First of all, the researcher will get formal approval for data collection in the institution.

- After ethical clearance, data will be collected through a case sheet of the patient and record of ERCP procedure at the department using prepared Per forma.
- Data of procedure outcome will be collected via call to the patient. Before collecting information from the respondent, they will be informed about the objective of the study and will be assured of privacy and volunteering participation.

B.8.1. Data Collection Tools/ Measures:

- Clinical Proforma will be used to collect data

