B15.1 Management of specimen/data archiving or left-over

NA

B15.2 Specimen/data sharing plan

NA

C. ETHICAL CONSIDERATION

10.1. Ethical issues	Yes/ No	Justification if yes
a. Are human participants included in the study?	Yes	The study aims to determine the clinico-demographic profile of the patients with cholangiocarcinoma undergoing ERCP in Dhulikhel Hospital. But we will not have face to face interaction, as all the information will be obtained from the medical records.
b. Are vulnerable members of the population required for this research? (includes age under 18, pregnant women etc)	No	
c. Are there any risks involved for the participants? If yes, identify clearly what are the expected risks for the human participants in the research and provide a justification for these risks.	No	
d. Are there any benefits involved for the participants? If yes, identify clearly what are the expected benefits for the participants.	No	

C1. SIGNIFICANCE OF THE STUDY

- The study can reveal some risk factors associated with the particular disease i.e Cholangiocarcinoma. Thus, it can be regarded as a baseline study for conducting any intervention.
- It can also be used as a reference for future study purposes in similar types of study.

C2. BALANCE OF RISK AND BENEFIT

C2.1 Risk of the study and Preventive and alleviative measures for risk

C2.1. Risk management:	
Potential risks identified	Proposed measures to mitigate risks
1. No direct risk/harm to the study participants as medical records will be reviewed primarily for patient data collection.	NA
2. Information on the patient's current status will be gathered via telephone interview (only for the feasible cases) where they may have to spare a few minutes for the data, however, this will take only a few minutes.	Verbal consent will be taken and all the information will be provided to the participants if the interaction is required.

C2.3 Benefits of the study

The study will be helpful to the future researcher to base on this and plan further studies so that we can enhance the prevention and treatment processes.

C3. CONSIDERATION FOR VULNERABLE RESEARCH PARTICIPANTS

Check whether your study involves any of the following vulnerable research participants.

- Prisoners
- Pregnant women
- Mentally ill persons
- Cancer or terminally ill patients
- Neonates/infants/children (aged <18)
- HIV/AIDS patients
- Institutionalized persons e.g. military, students, etc.
- Others (please specify).....

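### The smoking and alcohol items have no former level, no reference time and no code for missing history, so ever-exposure may be understated and within-case associations distorted

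*Combined protocol and SAP*

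**What the plan says.** - **The form.** In the proforma, Part 1, "6. Smoking Habit" can only be answered yes or no. "7. Alcohol Intake" can be answered "a. Non-alcoholic", moderate or significant. Neither item gives a period, a definition or a not-recorded option. Part 2 does offer an unknown code, for surgical operability (item 11).
- **Why the items are collected.** A.8 states: "Its risk factors include primary sclerosing cholangitis, hepatitis, smoking, alcohol, obesity, inflammatory bowel disease, cirrhosis, etc". B.1 repeats the list. Of the seven factors named in A.8, only smoking and alcohol have an item of their own. C1 says: "The study can reveal some risk factors associated with the particular disease i.e Cholangiocarcinoma".
- **Where the items are used.** Both sit among the socio-demographic variables. They therefore enter the second specific objective in B.4 (the demographic profile) and, on the natural reading, the fourth: "To identify the association between demographic variable and clinical presentation of the patient with cholangio-carcinoma undergoing ERCP". B.10 plans chi-square tests for categorical data.
- **How the data arise.** B.6.2 says: "The outcome and the exposure will be measured at the same time as a snapshot". B.8 takes the data from existing case sheets and ERCP records, and B.13 has the co-authors collect them. The telephone call is described only for procedure outcome and current status (B.8, C2.1, C4).

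**The concern.** A patient who smoked for decades and has stopped fits neither answer to item 6 clearly. One co-author may code yes, as a smoking history, and another no, as a non-smoker now. The same applies to a former drinker under item 7. B.1 places the disease mainly in the fifth to seventh decade of life, so a past habit is plausible for some patients.

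If former users go into the unexposed group, two results suffer. The reported share of ever-exposed patients falls below the true share. In the association tables, the unexposed group becomes a mixture of never and former users. If patients stop because of the illness, and do so more with some presentations than others, the coding itself can create, hide or reverse an association. Once the charts have been abstracted on the present codes, the split can be recovered only by reopening them.

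**Working it through.** The documents give no smoking or alcohol prevalence, effect size or significance level, so there is no planned figure to reproduce. The only input from the documents is the sample size of 375 (B.7.5), used as a denominator for counts. Everything else below is assumed.

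**1. Share reported as exposed**

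Let E be the true ever-exposed share, q the share of those who have stopped, and c the share of stoppers coded unexposed.

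- Reported share = E × (1 − q × c)
- Shortfall = E × q × c

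| E | q | c | Reported | Shortfall | Patients of 375 |
|---|---|---|---|---|---|
| 50% | any | 0 | 50% | 0 points | 0 |
| 50% | 20% | 1 | 40% | 10 points | about 37 |
| 50% | 40% | 0.5 | 40% | 10 points | about 37 |
| 50% | 40% | 1 | 30% | 20 points | 75 |
| 50% | 50% | 1 | 25% | 25 points | about 94 |
| 50% | 60% | 1 | 20% | 30 points | about 112 |
| 30% | 20% | 1 | 24% | 6 points | about 22 |
| 30% | 60% | 1 | 12% | 18 points | about 68 |

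For scale, the 95% half-width of a reported 40% is 1.96 × √(0.40 × 0.60 / 375) = 5.0 points. A 10-point shortfall is about twice that. The same formula serves alcohol if former drinkers are put in the lowest level.

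**2. Association, miscoding unrelated to presentation**

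Assume a symptom is present in 40% of never-smokers and the true odds ratio is 2.0. The odds in ever-smokers are 2.0 × 0.40/0.60 = 1.333, a risk of 0.571. Assume former and current smokers share that risk and all former smokers are coded no.

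Risk in the no group = [(1 − E) × 0.40 + E × q × 0.571] / [(1 − E) + E × q]

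For E = 50% and q = 20%: (0.200 + 0.057)/0.60 = 0.429, odds 0.75, so the observed odds ratio is 1.333/0.75 = 1.78. The other cases follow in the same way:

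| E | q = 20% | q = 35% | q = 50% |
|---|---|---|---|
| 50% | 1.78 | 1.67 | 1.58 |
| 40% | 1.84 | 1.75 | 1.68 |

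**3. Association, miscoding related to presentation**

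Assume half the patients are ever-exposed and a feature is present in 60% of ever-exposed and 45% of never-exposed patients. As shares of all patients, the cells are 0.300 and 0.200 (exposed, with and without the feature) and 0.225 and 0.275 (unexposed). True odds ratio = (0.300 × 0.275)/(0.200 × 0.225) = 1.83. Let s1 and s0 be the shares of exposed patients coded as exposed, with and without the feature.

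- s1 = s0 = 0.6: (0.180 × 0.355)/(0.120 × 0.345) = 1.54
- s1 = 0.5, s0 = 0.8: (0.150 × 0.315)/(0.160 × 0.375) = 0.79
- s1 = 0.8, s0 = 0.5: (0.240 × 0.375)/(0.100 × 0.285) = 3.16

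The first case also costs power. With 375 patients, two-sided 5% (assumed) and the usual normal approximation, 60% v 45% in 187.5 patients each has power of about 83%. After miscoding the comparison is 60.0% v 49.3% in 112.5 and 262.5 patients, with power of about 48%.

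**The case against.** Several points on the other side are fair.

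- **The form does not say current smoking.** A reader might infer from the word habit that only present use counts and that both exposures are therefore certain to be understated. The documents do not support this. The item has no tense or period, and a chart noting an ex-smoker could as readily be coded yes. If every former user is coded exposed, the shortfall in ever-exposure is zero. What stands is that the reference time is undefined.
- **Bias toward no effect is not assured.** It holds only when miscoding is unrelated to presentation. Stopping because of illness may not meet that condition, and nothing in the documents says how often it happens in these patients.
- **Little depends on it.** The study is descriptive, B.3 gives no hypothesis, and the fourth objective does not name smoking or alcohol. B.12 concedes that retrospective records may not hold all the information sought. This limits the weight of the point but does not remove it, because both items are on the form and C1 speaks of revealing risk factors.
- **The form is not final.** B.8.2 plans a pretest on about 10 cases, after which the proforma may be modified. No change to these items is stated, and few former users may appear among 10 charts.

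**Conclusion.** The concern holds as a limited weakness in two items of the form. As written, the proforma cannot separate former from never or current users, and coding may differ between co-authors.

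Ever-exposure in the profile may be understated, by anything from zero to the full share of former users. With 50% ever-smokers, 20-50% of them stopped and all of those coded no, 40% to 25% would be reported. Under those assumptions, an odds ratio of 2.0 with a symptom would be seen as 1.78 to 1.58, provided miscoding is unrelated to presentation and former and current smokers carry the same risk. If miscoding depends on presentation, the bias can go either way: 0.79 or 3.16 from a true 1.83 in the cases shown. All these inputs are assumed. The odds ratios are framed for smoking, and no separate calculation was made for the three-level alcohol item.

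A reader might also take C1 to mean that better coding would let the study estimate how far smoking or alcohol raises the risk of cholangiocarcinoma. It would not. All participants are cases, so that effect cannot be estimated however the items are coded. What is at stake is the descriptive profile and the associations among cases. The change is a cheap improvement and does not decide whether the study is sound.

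**What to change.** Before the B.8.2 pretest:

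1. Code item 6 as never, former, current or not recorded.
2. Add former and not recorded to item 7.
3. State on the form that both items refer to the time before the first symptom of this illness, where the chart allows. A patient who stopped because of the illness is then still counted as a user.
4. For the second and fourth specific objectives, report ever versus never, with the number not recorded beside each table.

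The not-recorded code is essential. Without it, silent charts would tend to be coded never, which restores the mixture that the change is meant to remove.

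The cost is two changed code lists and no new data source. Some charts will be silent on past use or on timing, so the denominators for these items will be smaller. A single former level for alcohol merges former moderate and former heavy drinkers. That does not affect ever versus never, but it leaves open the separate matter that moderate and significant are undefined.

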5. EUS FNA

- a) Yes
- b) No

6. If Yes

- 1) Positive
- 2) Negative

7. Brush cytology

- a) Yes
- b) No

8. If Yes

- 1) Positive
- 2) Negative

9. Intra ductal biopsy

a) Yes

b) No

10. If Yes

- 1) Positive
- 2) Negative

11. Surgical operability

- a. Operable
- b. Non-operable
- c. Unknown

12. Lab reports

- a) Total bilirubin.....
- b) Direct bilirubin.....
- c) ALP.....
- d) GGT.....
- e) AST.....
- f) ALT.....
- g) PT.....
- h) INR.....

13. Type of growth

- a. Distal
- b. Hilar

1) Bismuth-I

2) Bismuth-II

3) Bismuth-III

4) Bismuth-IV

5) Bismuth-V

Part 3. Outcome of ERCP procedure

14. Type of stent used in ERCP:

- a) Plastic stent
- b) Metal stent (SEMS)

15. Outcome of Stenting

- a) Immediate
- b) Failed Stenting
- c) Successful stenting

16. Complications

- a) Perforation
- b) Bleeding
- c) PEP
- d) PEC

17. If PEP done

- 1) Within 2 weeks
- 2) After 2 weeks

18. If PEC done

- 1) Within 2 weeks
- 2) After 2 weeks

19. Restenting

- a) Yes
- b) No
- 1) Within 1 month
- 2) Within 2 month
- 3) Within 3 month

20. Radio- Frequency Ablation

- Yes
- No

21. Survival Rate

- a) < 1 month
- b) 3-6 month
- c) 6 month- 1 year
- d) >1 year

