 - Part I: Socio-Demographic information of patient
 - Part II: Information related to Clinical profile of patient
 - Part III: outcome of ERCP procedure
- The data will then be entered into Microsoft Excel for further data management.

B.8.2. Pretesting

The proforma will be pretested entering about 10 cases so that we can further modify the proforma.

B.8.3. Validity and Reliability of tool

The tool will be the proforma and this will be based on other literatures and as per the experts suggestion. Indeed, the principal investigator is the physician (expert) to perform this procedure in Nepal and other team members have some kind of exposure in this sector.

B.9. Plan for specimen/data management:

(a) Data Processing

- Collected data will be stored in a file to prevent loss or damage.
- Data will be coded and entered in Microsoft Excel Sheet and will be transferred to the Statistical Program for Social Science (SPSS) for further analysis.

(b) Presentation of Data

- Data will be categorized on the basis of research objectives.
- The study will present the descriptive statistics and other details of the variables.

B.10. Plan for data analysis:

B.10. a. SPSS (Statistical Program for Social Science) version 25.0 will be used for descriptive as well as inferential statistics.

B.10. b. Statistical tests: Descriptive statistics (mean, frequency, standard deviation and percentage) will be applied. For inferential statistics, Chi-square test will be used for the analysis of the categorical data while, t-test or correlation will be done for the continuous variables.

B.11. Potential Biases:

There may be some confounders that will direct to the bias of the study. The information in the confounders will be collected and if required will be adjusted in the data analysis.

B.12. Limitations of the study:

- This is not a common disease, so the sample size of the eligible participants is limited.
- The retrospective study nature of this study may not allow us to incorporate as much information as we are seeking. However, future research may address these issues.

B.13. Plan for supervision and monitoring:

- Data will be collected by the co-authors
- Supervision and monitoring will be done by Principal Investigator and the research team

B.14. Plan for dissemination of the research:

The research will be disseminated to:

- Conferences
- Publication in one of the index peer review journal

B.15. DATA AND SPECIMEN BANKING AND/OR SHARING

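### The complications item has no code for none, not documented or other, so the ERCP complication percentage has no defined denominator and depends on how blanks are read

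*Combined protocol and SAP*

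**What the plan says.** The third specific objective (B.4) is "To measure the outcome of ERCP procedure in them". Part 3 of the proforma is the tool for it, and the item "16. Complications" is the only one that records which complication occurred. Its list starts with "a) Perforation" and continues with bleeding, PEP and PEC. It then ends, with no instruction on multiple answers. Items 17 and 18 ask whether PEP and PEC fell within or after two weeks.

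Other items on the form do carry negative or unknown codes. Items 5, 7, 9, 19 and 20 have yes and no, and item 11 (surgical operability) has an unknown option.

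B.8 names two sources. The first is the chart: "data will be collected through a case sheet of the patient and record of ERCP procedure at the department using prepared Per forma". The second is the telephone: "Data of procedure outcome will be collected via call to the patient". The risk table in C2.1 restricts calls: "only for the feasible cases". B.10 plans frequencies and percentages without a denominator or a rule for blank items. B.12 says of the retrospective design that it "may not allow us to incorporate as much information as we are seeking". B.8.2 provides for a pretest on about 10 cases, after which the proforma may be changed.

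**The concern.** On the form as printed, a blank at item 16 can mean three things: the record was reviewed and showed no complication, no post-procedure information was found, or an event occurred that is not on the list. The abstractor has no way to say which. Two analysts who both follow B.10 could then report very different percentages from the same data.

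The absence of a multiple-answer rule adds a smaller ambiguity. For a patient with both bleeding and PEP, the form does not say whether to enter one code or two, so the count could be of patients or of events.

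At stake is the safety figure for the procedure under the third specific objective. Once the forms are filled in, blanks can be resolved only by going back to the charts.

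**Working it through.** **Inputs from the documents.** The plan states no complication rate and no expected share of missing records, so there is no figure of its own to reproduce for this item. The only number available for scale is the estimated sample size of 375 (B.7.5). It equals 75 cases per year × 5 years; the stated window, January 2017 to January 2023, is about 6 years and would give 75 × 6 = 450. That mismatch does not affect the percentages below.

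**Assumptions (mine).** True complication rate *p* = 5%, 10% or 15%. Share of *complications* left undocumented *u* = 10%, 25% or 40%. The share that matters here is the one among patients with a complication: if every complication is documented, *u* = 0 and reading blanks as none does no harm, however many uncomplicated patients lack notes.

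**Reading A: blank means no complication.** Observed rate = *p* × (1 − *u*).

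| *p* | *u* = 10% | *u* = 25% | *u* = 40% |
|---|---|---|---|
| 5% | 4.5% | 3.75% | 3.0% |
| 10% | 9.0% | 7.5% | 6.0% |
| 15% | 13.5% | 11.25% | 9.0% |

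The relative understatement equals *u*.

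**Reading B: blank means missing and leaves the denominator.** Take *p* = 10%, *u* = 20%, N = 375. Recorded complications = 375 × 0.10 × 0.80 = 30, and blanks = 375 − 30 = 345. Only patients with a complication have a value, so the rate of any complication is 30/30 = 100%. Reading A on the same data gives 30/375 = 8.0%.

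**With separate codes.** Let 20% be undocumented among complicated and uncomplicated patients alike. Documented patients = 375 × 0.80 = 300, and undocumented = 75. The documented-only rate is 30/300 = 10.0%, the assumed truth. Counting the 75 as none gives 30/375 = 8.0%; counting all 75 as complicated gives (30 + 75)/375 = 28.0%.

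**When documentation depends on the outcome.** Documented-only rate = *p*(1 − *u*c) / [*p*(1 − *u*c) + (1 − *p*)(1 − *u*n)], where *u*c and *u*n are the undocumented shares among complicated and uncomplicated patients. With *p* = 10%:
- *u*c = 5%, *u*n = 20%: 0.095 / (0.095 + 0.720) = 11.7%. Undocumented share = 0.005 + 0.180 = 18.5%, so the bounds are 9.5% and 28.0%.
- *u*c = 20%, *u*n = 5%: 0.080 / (0.080 + 0.855) = 8.6%. Undocumented share = 0.020 + 0.045 = 6.5%, so the bounds are 8.0% and 14.5%.

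The new codes alone do not remove the bias in these two cases, but the bounds contain the assumed 10% in both.

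**The case against.** A reader might infer that missing records will be counted as complication-free and that the reported rate is therefore biased downward. The documents do not support that as a fact. No section says how a blank is read, and treating blanks as missing would push the rate the other way. Downward bias needs two conditions: blanks taken as none, and some complications undocumented. Since 100% would look absurd, reading blanks as none is the likelier default, but that is a judgement about analysts and is not in the plan.

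A reader might also infer that death is not captured. Item 21 does have a survival category below one month. It gives no cause, no link to the procedure and no alive-or-dead status, so it records early death only in part and cannot supply procedure-related death.

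Nor does B.12 admit that post-ERCP notes are incomplete. It is a general and conditional limitation, and the documents give no figure for missing notes.

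Three further defences have weight. First, telephone follow-up is aimed at procedure outcome and could fill gaps. But it is limited to feasible cases, C4.a describes it as a check on patient status, B.7.1 says patients will not be contacted directly, and no informant is named for patients who have died. An unsuccessful call leaves the same blank. Second, the form is to be pretested and may be revised. That makes the repair easy, but nothing commits the authors to it. Third, the charts remain and forms carry a serial number, so a blank could be rechecked. That is possible but costly: in the example above, 345 charts.

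**Conclusion.** The point holds as a defect of the form and of the analysis plan: item 16 cannot distinguish no complication from no information, and the percentage for the third specific objective has no defined denominator. The direction of any error is not fixed by the documents. If blanks are read as none, the understatement equals the undocumented share of complications, so an assumed 10% falls to 9.0%, 7.5% or 6.0% at shares of 10%, 25% and 40%. If blanks are read as missing, the rate is 100% by construction. The true rate and the undocumented shares are assumptions; the documents give neither. The telephone calls and item 21 are partial remedies only. The repair is cheap before abstraction and laborious afterwards, so it should be made.

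**What to change.** At the pretest revision foreseen in B.8.2:

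- Replace item 16 by one line per complication, each coded yes, no or not documented, with several allowed per patient.
- Add a line for other complications, and one for death within 30 days of ERCP with its relation to the procedure.
- State in B.10 that the main rate counts patients with at least one complication among those with documented status. Report the number undocumented beside it.
- Add a lower bound counting undocumented patients as uncomplicated and an upper bound counting all of them as complicated.

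The cost is a few boxes, slightly more abstraction work per chart, and possibly a less favourable rate. The codes make undocumented cases visible; they do not remove bias if documentation depends on whether a complication occurred. For that reason both bounds are needed.
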